12.3. Vital Signs

Descriptive statistics for blood pressure, heart rate, respiratory rate, and temperature including baseline values and change from baseline values, will be summarized by time point for each rare CKD cohort.

12.4. Body Weight

Descriptive statistics for body weight that are collected on the eCRF and change from baseline values will be summarized by time point for each rare CKD cohort. In addition, number and percentage of patients who experience a five-pound (2.3 kilogram) or greater increase in weight will be summarized by time point. Boxplot and line graphs of change from baseline over time for weight will be plotted. Summary tables for body weight will be repeated for the following subgroups:

- Weight change will also be summarized by baseline BMI (>30 and ≤ 30 kg/m²), and
- Baseline age (>18 and ≤ 18).

12.5. 12-lead ECG

Electrocardiogram (ECG) data, such as clinical interpretation of ECGs, ventricular rate and interval assessments of PR, QRS, QT, and QTcF, will be collected on the eCRF. Descriptive statistics for observed values and change from baseline at each time point will be presented for these 12-lead ECG interval assessments by rare CKD cohort. In addition, number and percentage of patients with any abnormal values (i.e., above a pre-specified threshold) will be summarized by time point and overall while on study drug. The pre-specified levels of ECG QTc thresholds are consistent with FDA guidance.

Table 9: Pre-Specified Threshold Levels for ECG Parameters

ECG Parameter	Pre-Specified Level
PR	>200 msec
QTcF	>450 , >480 or >500 msec >30 or >60 msec increase from baseline
Heart rate	<40 , >100 beats/min

Any results that exceed the above levels (provided in the above table) will be flagged in the listing.

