#### 8.5.1. Patient Discontinuation Criteria

Discontinuation refers to a patient's stopping administration of study drug. Reasons for study drug discontinuation may include the following:

- Occurrence of an AE or change in medical status that leads the investigator to be concerned about the patient's welfare
- Administrative reasons (e.g., inability to continue)
- Sponsor termination of the study
- Voluntary withdrawal
- Females who become pregnant during the study

Patients must discontinue study drug if any of the following occur.

- ALT or AST > 8X ULN;
- ALT or AST > 5X ULN for more than two weeks;
- ALT or AST > 3X ULN and (total bilirubin > 2X ULN or INR > 1.5);
- ALT or AST > 3X ULN with the appearance of fatigue, nausea, vomiting, right upper quadrant pain or tenderness, fever, rash, and/or eosinophilia (> 5%).

Patients who are discontinued from study drug should still continue in the study, complete all study visits, and undergo all scheduled study assessments, if possible.

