## 9.1.1. Management of Fluid Status

Specific risk mitigation procedures will be employed to reduce the potential for bardoxolone methyl-induced fluid overload. These procedures include exclusion of patients with any severe renal disease, defined as an eGFR value of < 30 mL/min/1.73 m^2. To exclude patients with significant cardiac dysfunction, the study will exclude patients with a history of left-sided heart disease. Patients who have evidence of volume overload at baseline, defined as BNP level of > 200 pg/mL, will also be excluded.

Laboratory data will also be used to monitor fluid status after randomization. Patients that experience a BNP > 100 pg/mL that represents a doubling (or more) of BNP levels from Day 1 should be instructed to stop taking their study medication immediately and return to the clinic within 1 week (± 3 days) for an unscheduled physical examination and laboratory assessment by the investigator.

Additionally, after randomization patients will be closely monitored for rapid weight gain suggestive of fluid overload. Patients will be given a Sponsor-provided scale to use at home to collect and record their weights daily during the first 8 weeks of the treatment period and weekly thereafter. Patients who experience a five-pound (2.3 kilogram) or greater increase in weight since their Day 1 weight during the first 8 weeks will be instructed to stop taking their study medication immediately and return to the clinic for an unscheduled physical examination and laboratory assessment by the investigator.

Investigators are encouraged to start or increase doses of diuretics (thiazides, loop diuretics) early after recognition of edema. This can be done concurrently with temporary drug discontinuation and re-initiation. Patients may not restart their study medication until the investigator has completed and documented an assessment of fluid overload.

Patients who experience a five-pound (2.3 kilogram) or greater increase in weight after the Week 8 study visit will be instructed to return to the clinic for an unscheduled physical examination and laboratory assessment by the investigator. Study medication should not be discontinued until the investigator has completed and documented an assessment of fluid overload.

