12.2. Clinical Laboratory Evaluation

Clinical laboratory test (serum chemistry [including NT-Pro BNP, BNP, IGF-1 and serum ketones], hematology [including hematocrit, hemoglobin (Hgb), red blood cell (RBC) count, white blood cell (WBC) count, neutrophils, bands (if detected), lymphocytes, monocytes, basophils (if detected), eosinophils (if detected), absolute platelet count, mean corpuscular hemoglobin (MCH), mean corpuscular volume (MCV), and mean corpuscular hemoglobin concentration (MCHC)], spot urine, and urinalysis of pH and specific gravity) results from the

central laboratory, where available, will be summarized by rare chronic kidney disease cohort using descriptive statistics at each scheduled time point. Laboratory assessments below LLD will be imputed as LLD/2. Laboratory assessments above the ULD will be imputed as the ULD. Changes from baseline will also be summarized by time point. Summaries of ACR will use the geometric mean with 95% confidence intervals instead of the arithmetic mean, and will display ACR results in units of mg/g. Changes from baseline in ACR will be reported as the post-baseline/baseline ratios and will be summarized by geometric means with 95% confidence intervals at each time point. Mean ratios of natural log(ACR)/eGFR will also be summarized at each time point. The ratio of natural log(ACR)/eGFR by analysis visit will be summarized by arithmetic means. Box plot graphs and line graphs may be generated for selected laboratory tests, such as ACR, ALT, AST, BUN, uric acid, magnesium, and creatinine. Line graphs will include mean \pm SE over time for both the observed values and for the change from baseline values.

Additional summary tables will be provided that includes that number and percentage of patients meeting the following 1) pre-specified threshold level at any time during the study (Table 7) and 2) ULN thresholds at any time during the study (Table 8).

Table 7: Pre-Specified Threshold Levels for Categorical Laboratory Summaries

Lab Parameter	Pre-Specified Level
ACR	> 3500 mg/g
Magnesium	< 1.3 mEq/L (0.65 mmol/L)
BNP	> 200 pg/mL
ALT, AST	> 3 \times upper limit of normal (ULN)
ALT, AST	> 8 \times ULN
ALT, AST	> 5 \times ULN for more than 2 weeks
ALT, AST, TBL, INR	> 3 \times ULN and (TBL > 2 \times ULN or INR > 1.5 \times ULN)

Table 8: Pre-Specified Upper Limit of Normal (ULN) Levels for Laboratory Parameters

Lab Parameter	Sex	Age	ULN
ALT	Female	All	34 U/L
	Male	All	43 U/L
AST	Female	< 18	40 U/L

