		\geq 18	34 U/L
	Male	< 18	40 U/L
		\geq 18	36 U/L
TBL			Central lab ULN
INR			Central lab ULN

Urinalysis results other than pH and specific gravity will not be summarized. Results not summarized include of ketones, protein, blood, glucose, clarity, color, leukocytes, nitrite,

bilirubin, and microscopic examinations (if indicated based on laboratory results), urine microscopic findings, and pregnancy test results will not be summarized.

Laboratory results that are above or below normal limits will be flagged in the listings.

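### Minor: the INR term in SAP Table 7 departs from the protocol's stopping rule, and SAP 12.4 gives no any-time count of a 2.3 kg weight gain

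*SAP*

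**What the plan says.** Safety after 12 weeks is a primary objective (Protocol 6.1, SAP 4.1.1).

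**Liver.** Protocol 8.5.1 requires permanent discontinuation for "ALT or AST > 3X ULN and (total bilirubin > 2X ULN or INR > 1.5"; Protocol 9.1.2 repeats the rule. The INR limit is an absolute value. The combined hepatic row of SAP Table 7 reads "ULN and (TBL > 2 \times ULN or INR > 1.5 \times ULN", and Table 8 gives the INR limit as "Central lab ULN" with no number.

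**Weight.** Protocol 9.1.1 has this trigger for stopping drug at once: "Patients who experience a five-pound (2.3 kilogram) or greater increase in weight since their Day 1 weight during the first 8 weeks". Patients weigh themselves at home daily over that period, and Protocol 9.10.7 keeps diary weights out of the eCRF. SAP 12.4 summarizes eCRF weights, and for the threshold says that the "number and percentage of patients who experience a five-pound (2.3 kilogram) or greater increase in weight will be summarized by time point". For ECG thresholds, SAP 12.5 says the count "will be summarized by time point and overall while on study drug".

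**BNP.** Protocol 9.1.1 says: "Patients that experience a BNP > 100 pg/mL that represents a doubling (or more) of BNP levels from Day 1 should be instructed to stop". SAP Table 7 counts BNP above 200 pg/mL, the level that Protocol 9.1.1 itself uses to define volume overload at baseline.

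**The concern.** Fluid overload is the risk for which the protocol sets specific mitigation, and a reader of the study report will want to know how many patients ever gained 2.3 kg. A table by visit does not answer that, and SAP 12.4 asks for nothing more.

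The INR term looks like a drafting slip. Other Table 7 rows carry the protocol's liver rules over unchanged, including "ALT or AST > 5X ULN for more than two weeks" and the row for more than 8 times ULN. Only the INR limit has gained a multiplication by ULN. If the ULN is above 1.0, a patient who had to stop drug through the INR limb could be missing from the row that appears to count that rule.

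**Working it through.** There is no stated figure in the plan to reproduce. The check sets each rule against its summary and works out what the difference can do.

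**1. INR.** The protocol cut-off is 1.5 (8.5.1, 9.1.2). The SAP cut-off is 1.5 × ULN. The ULN is not given, so a range is assumed:

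- ULN 1.0: 1.5 × 1.0 = 1.50, no difference
- ULN 1.1: 1.5 × 1.1 = 1.65
- ULN 1.2: 1.5 × 1.2 = 1.80

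The patients affected have ALT or AST above 3 times ULN, bilirubin not above 2 times ULN, and an INR between the two cut-offs. Protocol 5.1.2.2 reports transaminases above 3 times ULN in about 4% to 11% of patients in earlier studies. In a cohort of 25 that is 0.04 × 25 = 1 to 0.11 × 25 = 2.75 patients, before any INR condition applies. INR is also absent from the scheduled chemistry panel (Protocol 9.10.20); Protocol 9.1.2 calls for it when ALT or AST exceeds 5 times ULN. The number affected is therefore small and may be zero.

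Protocol 8.5.1 lists four liver rules. Table 7 carries three: two unchanged and one with the altered INR term. The fourth (above 3 times ULN with symptoms or eosinophilia) has no row.

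**2. Weight.** Let c(v) be the number at or above 2.3 kg at visit v, and n the cohort size, about 25 (Protocol 7.2). The number over the threshold at any of the visits lies between

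- the largest c(v), if the same patients recur, and
- min(n, sum of c(v)), if they are all different.

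Clinic weights are scheduled at Weeks 1, 2, 4, 6 and 8 within the period of the stop rule. With invented counts:

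- 1 at each visit: from 1/25 = 4% to 5/25 = 20%
- 2 at each visit: from 2/25 = 8% to 10/25 = 40%

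These counts illustrate only that the by-visit table does not determine the any-time figure. They do not estimate an undercount.

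Whether unscheduled clinic weights enter the table is unclear. SAP 7 leaves unscheduled values out of summary tables unless stated otherwise, while SAP 7.3 assigns values to visits by study day and takes the closest. SAP 12.4 does not settle it.

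**3. BNP (pg/mL).** The protocol hold rule is above 100 and at least 2 × Day 1. The Table 7 row is above 200.

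- Day 1 of 40, then 110: 2 × 40 = 80, so the hold rule is met; no row counts it.
- Day 1 of 150, then 290: 2 × 150 = 300, so the hold rule is not met; Table 7 counts it.
- Day 1 of 40, then 210: both apply.

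Neither set contains the other, so the row cannot stand in for the hold rule.

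**The case against.** The strongest reply is that Table 7 was never meant to audit the stopping rules. It also holds ACR and magnesium levels that stop nothing, and neither document promises a count of patients meeting each trigger. That stands. A reader might infer that every stop rule should have a matching row, or that the BNP row is wrong. The documents do not support either reading: 200 pg/mL is the protocol's own level for volume overload, though stated for baseline, and SAP 12.2 also summarizes BNP change from baseline.

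A reader might also set five scheduled clinic weights against 55 days of home weighing (Days 2 to 56) and conclude that the SAP misses most of the signal. That gap comes from the protocol's choice to keep diary weights out of the eCRF, and no SAP wording can close it. The minimum content of an unscheduled visit (Protocol 9.7) lists diary review but not a clinic weight, so adding unscheduled weights helps only where one was taken.

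There is existing cover. Edema and fluid retention events are reviewed in aggregate (Protocol 11.7), diuretic changes for edema are to be reported (9.1.1), AE records include action taken (11.6), and reasons for discontinuing drug go in the eCRF (8.5). SAP 9.1 and 12.1.2 tabulate disposition and TEAEs leading to interruption or discontinuation, and SAP 7 provides patient listings. A count of clinic-weight gains or BNP rises could be made by hand from those listings. This lowers the stakes, but none of these routes is a tabulated count of patients who ever gained 2.3 kg, and none corrects the INR term.

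**Conclusion.** The point holds as a minor safety-reporting correction, in two parts. The INR term is wrong as written: it departs from the rule stated twice in the protocol. The effect is nil at a ULN of 1.0 and small otherwise; the ULN values used here are assumptions. The by-visit weight count is not an error, but it cannot give the proportion of patients who ever gained 2.3 kg, and an any-time count is a cheap improvement on a primary safety objective.

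Even the improved count would not be the number who met the stop trigger. Through Week 8 it is a lower bound on that number, because gains seen only at home are not in the data. The size of any shortfall cannot be derived from the documents. The BNP point is an optional addition. The primary efficacy analysis is unaffected.

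**What to change.** 1. **SAP Table 7.** In the combined hepatic row, replace the INR multiple of ULN with INR above 1.5, and drop the INR entry in Table 8 if nothing else uses it.
2. **SAP 12.4.** Keep the by-visit count and add the number and percentage of patients with a gain of at least 2.3 kg from Day 1 at any time, through Week 8 and overall, following the format of SAP 12.5. State that all eCRF clinic weights are used, including any unscheduled ones. Add a footnote that the Week 8 count is a lower bound on patients who met the stop trigger, because diary weights are not in the eCRF and an unscheduled visit need not include a clinic weight.
3. **Optional, SAP Table 7.** Keep BNP above 200 pg/mL and add a row for BNP above 100 pg/mL with at least a doubling from Day 1.

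The cost is SAP wording and minor programming, with no protocol amendment. Reported counts may be somewhat higher.

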12.6. Physical Examination

Abnormal clinically significant findings will be reported as Medical History or Adverse Events depending on date of onset. Abnormal non-clinically significant findings from physical examinations will be listed.

12.7. Analyses of Continuous eGFR and ACR

Additional safety endpoints will be evaluated by rare chronic kidney disease cohort:

- Change from baseline in eGFR at Week 16 following a 4-week drug treatment withdrawal period
- Ratio of natural log (ACR)/eGFR by analysis visit, for visits at Baseline through Week 16. The ratio of natural log(ACR)/eGFR by analysis visit will be summarized by arithmetic mean and standard deviation at each time point.
- Change from baseline in ACR summarized by baseline ACR category (ACR \leq 300, ACR > 300)

12.7.1. Change from Baseline in eGFR at Week 16

A mixed-model for repeated measures (MMRM) will be used to analyze the change from baseline eGFR at Week 16. The MMRM results will be reported by rare CKD cohort. The eGFR values collected closest to the target study day (Section 7.3) through the Week 16 visit will contribute to the analysis, and only patients who have completed the study through Week 16 will be included in the analysis. The change from baseline in eGFR value will be calculated for each post first dose time point through Week 16 visit (i.e., Weeks 1, 2, 4, 6, 8, 12, and 16). Missing data will not be imputed. The primary inference will be the test of LS mean at each time point. The MMRM model used will be that in Section 11.1.2.

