7.1.3. Estimated Glomerular Filtration Rate

Estimated glomerular filtration rate (eGFR) value will be calculated at the central laboratory and used in data analyses. The equation used to calculate eGFR for each patient will be the Chronic Kidney Disease Epidemiology Collaboration (CKD-EPI) equation:

- $eGFR \text{ (mL/min/1.73 m}^2\text{)} = 141 \times \min(S_{cr}/\kappa, 1)^\alpha \times \max(S_{cr}/\kappa, 1)^{-1.209} \times 0.993^{\text{Age}} \times 1.018 \text{ [if female]} \times 1.159 \text{ [if black]}.$

Where S_{cr} is serum creatinine (mg/dL), κ is 0.7 for females or 0.9 for males, and α is -0.329 for females or -0.411 for males. Min indicates the minimum of S_{cr}/κ or 1, and max indicates the maximum of S_{cr}/κ or 1.

Historical serum creatinine and eGFR values will be treated separately from data collected as part of the trial's central lab assessments. Historical eGFR values will be calculated from historical serum creatinine results.

Missing eGFR values will not be imputed for the primary analysis of efficacy. The eGFR values collected after the window of the date of last dose for patients who do not complete study treatment will not be included in the analysis.

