7.3. Analysis Windows

Because clinical visits may occur outside protocol specified windows, instead of relying solely on visit labels in the clinical database, analysis visits and their windows are defined using Study Day (See Section 7.1.2). Analysis visit windows are presented in Table 3 by type of assessments and/or measurements.

If more than one on-treatment assessments and/or measurements exists for a parameter within a visit window, the one that is closest to the protocol scheduled time point (or target Study Day) will be used for analysis and summary. If more than one off-treatment assessment exists, the one closest to the target study day will be used for analysis and summary.

Table 3: Analysis Windows

Visit Scheduled Time Point	Target Study Day	Analysis Visit Windows	
		All Other Assessments	12-lead ECG
Screen A	-60	-180 to -2	-180 to 1
Screen B ^a	-1	-30 to -1	-
Day 1	1	1	-
Week 1	7	2 to 10	-
Week 2	14	11 to 21	-
Week 4	28	22 to 35	-
Week 6	42	36 to 49	-
Week 8	56	50 to 70	-
Week 12	84	71 to 98	2 to 98
Week 16	112	> 98	-

^aScreen B is after Screen A, and no more than 30 days prior to Day 1

Note: Study Day is relative to the first date of study drug administration (Study Day 1). Visit Scheduled Time Point = Analysis Visit (AVISIT), after applying the analysis windows described above. The Week 16 visit has the additional restriction that assessments must be collected after last dose of study treatment. For patients who terminated treatment prior to Week 12, use Week 16 as follow-up visit.

If more than one measurement is collected equidistant to the target Study Day and on different collection date/time, the first measurement will be flagged for analysis and summary. If more than one measurement is closest to the target Study Day and collected on the same date, the average of those measurements will be used for analysis and summary.

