8.3. Off-Treatment Analysis Sets

The Week 16 off-treatment analysis set is defined as all randomized patients who were dosing compliant through Week 12 as defined by:

- Still taking study medication at the Week 12 in-person visit; and
- Had a Week 16 assessment.

The off-treatment analysis sets will be used for evaluation of off-treatment safety at Week 16.

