12. SAFETY ANALYSES

Safety and tolerability are evaluated by AEs, SAEs, clinical laboratory test results, body weight, vital signs, 12-lead ECG findings, physical examination, visual acuity, and audiology assessment. All analyses of the safety data will be performed using the safety analysis set. Descriptive statistics (described in Section 7) will be presented for the safety analysis set.

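### SAP 8.3 and SAP 12.7.1 give different populations for the Week 16 off-treatment eGFR analysis, and under 12.7.1 early drug stoppers may be pooled with patients about 4 weeks off drug

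*SAP*

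**What the plan says.** SAP 12.7 lists among the additional safety endpoints: "Change from baseline in eGFR at Week 16 following a 4-week drug treatment withdrawal period". The following passages bear on who is analysed.

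- **SAP 8.3** defines the Week 16 off-treatment set by two conditions: "Still taking study medication at the Week 12 in-person visit", and having a Week 16 assessment. It then gives the set its purpose: "The off-treatment analysis sets will be used for evaluation of off-treatment safety at Week 16".
- **SAP 12.7.1**, which specifies the model for this endpoint, says "only patients who have completed the study through Week 16 will be included in the analysis". It sets no condition on being on drug at Week 12 and does not mention the 8.3 set.
- **SAP 12** opens with a general sentence: "All analyses of the safety data will be performed using the safety analysis set".
- **SAP 9.1** treats completing treatment (through Week 12) and completing study visits (through Week 16) as separate things.
- **Protocol 8.5.1** says "Patients who are discontinued from study drug should still continue in the study, complete all study visits", and adds a proviso that this applies where possible.
- **SAP 7.3, Table 3** defines Week 16 as any Study Day above 98 and after the last dose, with no minimum or maximum time since that dose. Its note adds: "For patients who terminated treatment prior to Week 12, use Week 16 as follow-up visit".
- **SAP 7.1.3** removes from the analysis "eGFR values collected after the window of the date of last dose for patients who do not complete study treatment". It does not say whether this reaches the Week 16 safety model.

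**The concern.** A withdrawal endpoint is interpretable only if the time off drug, and preferably the exposure before it, is about the same for everyone. The 8.3 set secures this through its on-drug condition at Week 12. The completer rule in 12.7.1 does not. Two programmers who each follow the text could fit the Week 16 model to different patients, and nothing in the SAP says which section governs.

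The endpoint also matters for interpretation. Protocol 5.1.1 uses eGFR four weeks after withdrawal in earlier trials to argue for reversal of structural change. Those data came from patients treated for 52 weeks, or for at least 48. A Week 16 mean that includes patients with a few weeks of exposure and two or three months off drug could not be read in the same way.

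**Working it through.** **1. The plan's own interval.** The schedules of assessments (Protocol Table 5, SAP Table 2) put Week 12 at Day 84 ± 3 and Week 16 at Day 112 ± 3. Protocol 10.4 continues dosing up to the Week 12 visit.

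- Planned interval: 112 − 84 = 28 days = 4.0 weeks.
- Shortest within visit windows: (112 − 3) − (84 + 3) = 22 days.
- Longest within visit windows: (112 + 3) − (84 − 3) = 34 days.

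So the 4-week figure is reproduced for patients dosed to Week 12, the group that 8.3 selects. The Table 3 analysis windows are looser: with last dose on Day 84, a value on Day 99 qualifies at 99 − 84 = 15 days, and there is no upper limit.

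**2. Who qualifies under each rule.** Take a patient who stops drug on Day 28, stays in the study and attends on Day 112.

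| Rule | Included? | Reason |
|---|---|---|
| SAP 8.3 | No | Not on drug at the Week 12 visit |
| SAP 12.7.1 | Yes | Completed the study through Week 16 |
| SAP 12, general sentence | Yes | Received study drug |

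**3. Time off drug at Day 112 for early stoppers who keep the schedule.** Weeks off = (112 − day of last dose) / 7.

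| Last dose | Weeks off drug |
|---|---|
| Day 14 | 14 |
| Day 28 | 12 |
| Day 42 | 10 |
| Day 56 | 8 |
| Day 70 | 6 |
| Day 84 (planned) | 4 |

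**4. Average time off drug in a pooled cohort.** The documents give no early-stopping rate, so I assume k = 1 to 5 of 25 patients. Mean weeks = [(25 − k) × 4 + k × w] / 25, where w is the stoppers' time off drug.

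- Last dose Day 42 (w = 10): k = 1 gives 106/25 = 4.24; k = 5 gives 130/25 = 5.2.
- Last dose Day 14 (w = 14): k = 1 gives 110/25 = 4.4; k = 5 gives 150/25 = 6.0.

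**5. Illustrative shift in the Week 16 mean.** Protocol 5.1.1 reports retained increases of 4.0 and 4.3 mL/min/1.73 m² four weeks off drug, after 52 weeks of treatment at 75 and 150 mg in type 2 diabetes with CKD. I use these only to set a scale, and assume early stoppers sit at zero change. Shift = (k/25) × retained change.

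- k = 0: 0.
- k = 1: 0.04 × 4.0 = 0.16; 0.04 × 4.3 = 0.17.
- k = 5: 0.20 × 4.0 = 0.80; 0.20 × 4.3 = 0.86.

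These are shifts in a simple mean. The least squares mean from the repeated-measures model would differ somewhat because it adjusts for baseline eGFR and log ACR.

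**The case against.** Several points on the other side have force.

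- **Pooling is possible, not established.** A reader might infer that the Week 16 result simply is not a 4-week withdrawal effect. The documents do not support that. Under 8.3 it is one, and under 12.7.1 the departure depends on how many early stoppers attend, which Protocol 8.5.1 asks for only where possible.
- **Section 12 is a weak third contender.** A reader might count three rival populations. The Section 12 sentence is a general default, and treated patients meeting either narrower rule form subsets of the safety set. The live conflict is 8.3 against 12.7.1; Section 12 only adds ambiguity.
- **SAP 7.1.3 cannot be used both ways.** If it applies here, early stoppers' off-drug values are removed and the Week 16 pooling disappears. If it does not, it does not conflict with the Table 3 note. The preceding sentence in 7.1.3 concerns the primary efficacy analysis, and SAP 11.1 confines its matching rule to efficacy analyses, so the narrow reading is the more natural. The text should still say so.
- **The Table 3 note is ambiguous.** It might be taken to relabel an early follow-up visit, even one before Day 98, as Week 16. It can equally mean that the Week 16 visit serves as the stopper's follow-up, and it does not say that it overrides the above-Day-98 window. Patients who leave the study early would ordinarily not be completers under 12.7.1 anyway.
- **The illustration runs against the drug.** With stoppers at zero the mean falls, so pooling would understate retained benefit rather than inflate it. The documents do not establish the direction in practice.
- **The 8.3 set has its own selection.** It keeps only patients who stayed on drug to Week 12.

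What remains is the mismatch between 8.3 and 12.7.1, and the fact that 12.7.1 as written can admit patients whose time off drug is well beyond 4 weeks.

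**Conclusion.** The point holds in this limited form. The SAP gives two different membership rules for one endpoint, and the section that specifies the model uses the one that does not secure the stated withdrawal period. Under 12.7.1, early stoppers who attend Week 16 may be pooled with patients about 4 weeks off drug, so the estimate may not be the effect that SAP 12.7 names.

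The illustrated effect on the Week 16 mean is a fall of 0.16 to 0.86 mL/min/1.73 m² for 1 to 5 stoppers of 25, and zero if nobody stops early. It rests on an assumed number of stoppers, zero change in those patients, and a retained effect borrowed from much longer treatment in another population. This is an additional safety endpoint, and the Week 12 primary analysis does not depend on it.

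**What to change.** SAP Section 3 allows amendment before database lock. The changes are:

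1. In 12.7.1, replace the study-completer restriction with the Week 16 off-treatment set from 8.3, and state that this takes precedence over the general sentence in Section 12.
2. Require the Week 16 value to fall within a stated interval after the last dose that matches the planned 28 days and the visit windows (22 to 34 days).
3. State in 7.1.3 that its exclusion of post-discontinuation values applies to the efficacy analyses only.
4. Clarify the Table 3 note: say whether the Week 16 visit serves as an early stopper's follow-up or an earlier follow-up takes the Week 16 label, and whether the above-Day-98 window still applies.
5. Summarise early stoppers' follow-up eGFR separately, with time since last dose.

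The cost is SAP wording, a derived flag and one extra summary. The Week 16 model loses a few patients and its confidence interval widens slightly. The result will describe only patients who stayed on drug to Week 12, and the report should say so.
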